2.3 Exploratory Objectives

- 1) To investigate and compare incidence of anemia and renal impairment among AF patients in relation to INR levels: under 2.0, 2.0-3.0, and over 3.0.
- 2) To investigate risk of stroke, systemic thromboembolic events, myocardial infarction, and bleeding events among AF patients in relation to discontinuation of warfarin treatment due to surgical operations and interventions.
- 3) To investigate how long it takes to achieve INR target in treatment initiators.
- 4) To investigate how well the INR target is maintained (TTR level).
- 5) To characterize the use of antiarrhythmic medication in AF patients at start of warfarin use and during warfarin use.
- 6) To characterize the use of medications with known interactions with warfarin in AF patients at start of warfarin use and during warfarin use.
- 7) To characterize comorbidity in AF patients using warfarin.

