3.4 Definitions of Study Variables

3.4.1 Outcomes/Endpoint Variables

The studied primary outcomes/endpoint variables of interest are defined through ICD-10 diagnosis codes (hospitalizations and deaths) or ICD-O-3 codes (cancers). See [Appendix 1](#) and [2](#) for more detail.

The time to event for each primary outcome will be calculated as the time from the index date to the time of the diagnosis of the outcome when such an event occurs during the follow-up.

Index date is defined as the date of first purchase of warfarin after 01-Jan-2007. Follow-up of the patients starts on the index date, and ends on 31-Dec-2011, at time of death or at time of emigration whichever occurs first. Treatment and comorbidity history is gathered from the period 01-Jan-2005 to 31-Dec-2006.

Primary outcomes:

- Stroke
- Other systemic thromboembolic events excluding stroke
- Myocardial infarction
- Bleeding events
- Mortality all-cause
- Mortality (stroke)
- Mortality (myocardial infarction)
- Mortality (systemic thromboembolic events excluding stroke)
- Mortality (bleeding events)

The studied secondary outcomes/endpoint variables of interest are anemia and renal impairment.

Time to anemia is defined as the time from index date to time of first decrement of 20 g/L in haemoglobin or time when haemoglobin is under the reference value.

Time to renal impairment is defined as the time from index date to time when creatinine is under the reference value.

Secondary outcomes

- Anemia
- Renal impairment

In the statistical analysis follow-up for each time to event outcome continues until the time of the event, death, emigration or 31-Dec-2011 whichever comes first.

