4.1.3 Exploratory Objectives

Objective 1: Stratified incidence rates with 95% CIs will be estimated for anemia as endpoint within the strata of the exposure variables (INR levels and TTR categories) and other covariates.

The crude and adjusted hazard ratio (HR) estimates with 95% CIs and P-values will be estimated separately within the INR levels and TTR categories using the conventional Cox's proportional hazards model adjusting for other covariates. For INR the category 2.0–3.0 will be used as the reference category. Similarly for TTR the category $\geq 60\%$ of time will be used as the reference category.

Objective 2: Discontinuity period of warfarin treatment due to a surgical operation or intervention is identified as starting two weeks before and ending two weeks after such procedure.

Stratified incidence rates with 95% CIs will be estimated for stroke, systemic thromboembolic events, myocardial infarction, and bleeding events in the strata of other covariates within periods of warfarin discontinuity. Also, an indicator variable of the discontinuity period will be added to the Cox's proportional hazards model.

Sensitivity analysis will be done to study the robustness of the discontinuity period definition.

Objective 3: The distribution of days taken to achieve INR target in the new warfarin user population will be provided. Stable INR-target is considered achieved after 3 consecutive INR measurements are within the target 2.0-3.0.

Objective 4: For the new warfarin user population the distribution of TTR at 1, 6, and 12 months after start of warfarin treatment stratified by other covariates. For the prevalent warfarin user population the distribution of TTR at the end of 2010 and 2011 stratified by other covariates.

Objective 5: Warfarin users will be tabulated by use of antiarrhythmic medication (yes/no) at start of follow-up and during follow-up. During follow-up users will also be stratified by the INR and the TTR levels.

Objective 6: Warfarin users will be tabulated by use of interaction medication (yes/no) at start of follow-up and during follow-up. During follow-up users will also be stratified by the INR and the TTR levels.

Objective 7: Warfarin users will be tabulated by comorbidities.

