5 STUDY LIMITATIONS/STRENGTHS

Finland has a well-developed population register system with tens of years of longitudinal follow-up data. The persons are identified in the registers with a unique personal identification number enabling linkage between different registers. These data has not been collected for study purposes, which may affect the quality of the data. However, these registers have been considered reliable for scientific research purposes.

Only those citizens that have been living in Finland for 12 months prior to index date will be included in the study.

No exact prescribed dosing information is available. Dosing is assumed based on the information of purchases and package sizes with defined daily doses (DDDs).

Coverage of the Prescription Register containing reimbursement information of all permanent residents of Finland is about 97%. Missing data includes relatively inexpensive packages which are not reimbursed. Fully reliable information on eg, acetylsalicylic acid use is then not available.

Medications used during hospitalizations are not available. However, based on the hospital care register the hospitalization periods can be taken into account to define gaps in the drug treatment periods.

No nationwide database about laboratory measurements is available. The laboratory data is then collected from separate local central laboratories. All laboratory values for particular patients may then not be available. Also changes in places of domicile may affect the follow-up of the patients. On the other hand, previous published surveys on the subject have not included INR follow-up to this extend.

To avoid selection bias, the cohort time (years 2007 to 2009) was chosen to avoid complication of patients switching from warfarin to newer anticoagulant medications eg, dabigatran.

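### Exploratory objective 2 opens the warfarin discontinuity period two weeks before the procedure, so outcome events that prompt a procedure are counted as events during interruption

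*Protocol*

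**What the plan says.** Section 2.3 states the aim: risk of stroke, systemic thromboembolism, myocardial infarction and bleeding "in relation to discontinuation of warfarin treatment due to surgical operations and interventions". Section 4.1.3 turns this into a rule that applies to surgery and other interventions alike. The window is "identified as starting two weeks before and ending two weeks after such procedure". Incidence rates are then estimated "in the strata of other covariates within periods of warfarin discontinuity", and "an indicator variable of the discontinuity period will be added" to the Cox model.

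The rule does not separate planned from acute procedures, or time before the procedure from time after it. It does not require evidence that warfarin had been stopped before the event. It does not set aside procedures that follow an outcome event. The one safeguard is a single sentence: "Sensitivity analysis will be done to study the robustness of the discontinuity period definition". It gives no alternative windows.

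Three other provisions bear on the point. Section 3.4.1 takes the primary outcomes from hospital and death diagnoses and ends follow-up for each outcome at the event. Section 3.4.3 says that hospitalization dates will be used when discontinuation is defined. Section 5 concedes: "Medications used during hospitalizations are not available".

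**The concern.** The objective treats interruption as the exposure and the event as its possible consequence, so exposure has to come first. A window opened backwards from the procedure does not secure that order. Appendix 1 lists outcomes that can plausibly lead to an acute procedure: myocardial infarction (I21, I22), intracranial bleeding (I60-I62), ulcer and other gastrointestinal bleeding, and arterial embolism (I74). If such an event falls on day t and the procedure on day t+1 to t+14, the event lies inside the window although it caused the procedure.

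The Cox indicator has a related fault. Whether day t counts as exposed depends on a procedure up to 14 days later. A time-dependent covariate should use only what is known by day t. Conditioning on a later procedure also means that the patient must live to have it, and that a planned procedure must not be cancelled because of an event.

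At stake is whether the rates and hazard ratio for this objective can be read as the risk of interruption at all.

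**Working it through.** The protocol gives no power or expected rate for this objective, so there is no planned figure to reproduce. The calculation below illustrates only the upward mechanism.

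**Inputs from the protocol**
- Window: 14 + 14 = 28 days (Section 4.1.3).
- Background rates r: 1.5, 3 and 6 per 100 person-years (the rates used for power in Section 4.2).

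**Assumed inputs, not in the protocol**
- Procedures not prompted by an outcome, p: 5, 10 or 20 per 100 person-years.
- Share f of outcome events that prompt a procedure within 14 days: 1%, 5% or 10%.
- True effect of interruption: none.

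**Formulas, per 100 person-years**
- Window time W = (p + f·r) × 28/365.25.
- Events in the window E = f·r + (1 − f)·r·W/100.
- Apparent rate ratio = (E/W) ÷ [(r − E)/(100 − W)].

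**Worked case: r = 3, p = 10, f = 5%**
- W = (10 + 0.15) × 28/365.25 = 0.778 person-years.
- E = 0.15 + 0.95 × 3 × 0.00778 = 0.172 events.
- Rate inside = 0.172/0.778 = 22.1 per 100 person-years.
- Rate outside = (3 − 0.172)/(100 − 0.778) = 2.85 per 100 person-years.
- Ratio = 22.1/2.85 = 7.8, where the truth is 1.

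**Apparent rate ratio at r = 3**

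| p per 100 person-years | f = 1% | f = 5% | f = 10% |
|---|---|---|---|
| 5 | 3.6 | 14.3 | 28.3 |
| 10 | 2.3 | 7.8 | 15.1 |
| 20 | 1.7 | 4.4 | 8.1 |

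Over all three background rates the range is 1.7 to 29; the top value is for r = 1.5, p = 5, f = 10%. The ratio changes little with r, but only because f is defined per event.

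**Second parameterisation.** Let g be the share of windows whose procedure was prompted by an outcome (assumed). Background events per window are r/100 × 28/365.25 = 0.00115, 0.00230 and 0.00460 at the three rates. The apparent ratio is (background + g)/background.

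| g | r = 1.5 | r = 3 | r = 6 |
|---|---|---|---|
| 0.1% | 1.87 | 1.43 | 1.22 |
| 0.5% | 5.35 | 3.17 | 2.09 |
| 1% | 9.70 | 5.35 | 3.17 |

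The ratio doubles when g equals the background, that is at 0.11%, 0.23% or 0.46% of windows. The two versions agree: r = 3, p = 10, f = 1% gives g = 0.03/10.03 = 0.30% and a ratio of (0.00230 + 0.00299)/0.00230 = 2.3.

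**Follow-up ending at the event.** The first formula credits a full 28 days to each event-prompted window, although Section 3.4.1 stops follow-up for that outcome at the event. This matters little in the worked case, where such windows are 0.15/10.15 = 1.5% of the total. A different reading of the stop rule matters more. If procedures after the event open no window, the 14 days before every remaining procedure are event-free by construction. With no true effect the pooled window then holds 14 days at the background rate and 14 days at zero, a ratio of about 14/28 = 0.5.

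**The case against.** The strongest reply is that the protocol limits the objective to discontinuation caused by an operation, which does not naturally describe an event that caused the operation, and that Section 4.1 leaves detail to a separate SAP, which is not at hand. An SAP could restrict the eligible procedures. But the wording of the aim expresses intent only; the operative rule uses the procedure date and nothing else. Following an unsuitable rule is different from leaving a detail open. The hospitalization dates in Section 3.4.3 help to define treatment gaps but do not remove event-prompted procedures.

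Second, a robustness analysis is promised. A reader might infer that it cannot help because every alternative window would also open early. The protocol does not say so: a window starting on the procedure date would fit the sentence. What can be said is that the analysis is unspecified and is not stated to address this problem. Changing the width alone would not cure it while any pre-procedure time stays pooled.

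Third, the direction is not certain. Fatal events before a procedure, and events that cancel a planned one, leave no window and count as unexposed. This pulls the ratio down, as does the second reading of the stop rule. This objection stands.

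Fourth, warfarin may really be interrupted before a planned procedure, so the preceding fortnight can carry meaning. That is a reason to show it separately, not to pool it.

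**Conclusion.** The rule is faulty as written. It allows outcome events to precede and cause the exposure they are attributed to, and it defines exposure by a later procedure. The pre-procedure half of the window therefore cannot be read as risk during interruption.

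The net size cannot be derived from the protocol. The range of 1.7 to 29 describes the upward mechanism alone, under assumed procedure rates and event shares that may differ widely between stroke, infarction and the broad bleeding list. A reader might infer that the analysis is bound to show a large excess risk, or that its answer is bound to be wrong. The protocol does not support that: it gives neither the mix of procedures nor their frequency, and opposing biases are present. The illustration does show that well under 1% of windows being event-prompted is enough to double the apparent rate.

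The point concerns one of seven exploratory objectives. No primary or secondary analysis uses this window. It should be corrected, but it does not threaten the main INR comparisons.

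**What to change.** Amend exploratory objective 2 in Section 4.1.3, or settle it in the SAP before any analysis:

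1. Exclude from the main analysis procedures preceded by an outcome event in the same admission or within the previous 14 days.
2. Base the main rates and the Cox indicator on time from the procedure date to two weeks after. Do not use the admission date, because an event that caused the admission may carry that date and stay inside the window. State how an outcome dated on the procedure day is classed.
3. Report the two weeks before the procedure as a separate interval, never pooled with the time after, and label it as subject to this bias.
4. State how the end of follow-up at an event applies to later procedures, and name the windows to be used in the robustness analysis.

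The cost is wording and some programming, with no new data source. The downside is that genuine interruption before a procedure leaves the main estimate and appears only in the separate interval. The change concerns how time and events are counted and takes no position on how warfarin should be managed around procedures.

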4 STATISTICAL ANALYSIS

4.1 Statistical Analysis Methods

Data management, tabulations, graphics, and statistical modeling in carried out with R language (<http://www.r-project.org>). R language is described more detailed in report "R: Regulatory

Compliance and Validation Issues: A Guidance Document for the Use of R in Regulated Clinical Trial Environments" (<http://www.r-project.org/doc/R-FDA.pdf>)

A separate statistical analysis plan (SAP) including detailed statistical analysis and outputs will be produced by EPID research prior to performing any analysis.

Study population: The study population will be described at baseline (start of follow-up) using by previous drug exposure and other covariates.

Study outcomes: All study outcomes will be summarized by drug exposure and other covariates.

Drug exposure: Drug exposure starts at date of purchase. The length of the exposure period is calculated as $DDD/dose \times 1.5$, where DDD (daily defined dose) is the total amount purchased and “dose” is the amount used daily (one for an average person). For the first purchase “dose=1” and for other purchases the “dose” is calculated from previous use by dividing the previous DDD with the time between the present and the previous purchase.

The impact of the multiplier 1.5 in the construction of drug exposure will be evaluated for the primary objectives in sensitivity analyses by using multiplier values 1.25, 1.5 and 2. We will also perform a sensitivity analysis for the primary objectives by including only those patients with at least two purchases of prescriptions within a clinically meaningful timeframe of 3 months after the index date.

INR levels: Daily INR levels are calculated:

- 1) As the previous recorded INR measurement
- 2) By linear interpolation between two consecutive INR measurements. If the gap between the measurements is more than 60 days the previous measurement is applied.

Daily INR estimates are categorized into levels: under 2.0, 2.0-3.0, over 3.0. In addition when appropriate a finer categorization is used: under 1.5, 1.5-2.0, 2.0-3.0, 3.0-4.0, 4.0-5.0, 5.0-9.0, and over 9.0. This finer categorization will be used only in the analysis of the primary objectives.

Time in therapeutic range (TTR): The INR target value for AF patients is 2.0-3.0. In addition for stroke, systemic thromboembolic events, and myocardial infarction INR target above 2.0 is considered and for bleeding events INR target under 3.0 is considered.

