4.1.1 Primary Objective

Objectives 1-3: Stratified incidence rates with 95% confidence intervals (CIs) will be estimated for each primary endpoint within the strata of the exposure variables (INR levels and TTR categories) and other covariates, including history of AF prior the index date.

The crude and adjusted hazard ratio (HR) estimates with 95% CIs and P-values will be estimated separately within the INR levels and TTR categories using the conventional Cox's proportional hazards model adjusting for other covariates. For INR the category 2.0–3.0 will be used as the reference category. Similarly for TTR the category $\geq 60\%$ of time will be used as the reference category.

The objectives will be evaluated separately for the prevalent warfarin user population and the new warfarin user population. The new warfarin user population consists of those patients who initiate warfarin treatment during the follow-up (01-Jan-2007 to 31-Dec-2009).

A further sensitivity analysis will be performed where the adjusted HRs are estimated stratifying by the history of AF prior to the index date.

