4.1.2 Secondary Objectives

Objective 1: Stratified incidence rates with 95% CIs will be estimated for stroke, systemic thromboembolic events, myocardial infarction, and bleeding events within the strata of the exposure variables (INR levels and TTR categories) and other covariates during the first 90 days after initiation of warfarin treatment.

The crude and adjusted hazard ratio (HR) estimates with 95% CIs and P-values will be estimated separately within the INR levels and TTR categories using the conventional Cox's proportional hazards model adjusting for other covariates, including history of AF prior the index date. For INR the category 2.0–3.0 will be used as the reference category. Similarly for TTR the category $\geq 60\%$ of time will be used as the reference category.

Objective 2: Stratified incidence rates with 95% CIs will be estimated for stroke, systemic thromboembolic events, myocardial infarction, and bleeding events within the strata of the exposure variables (INR levels and TTR categories), and time from AF diagnosis to time of initiation of warfarin treatment (categories: under 6 months, 6-12 months, over 12 months). For INR the category 2.0–3.0 will be used as the reference category. Similarly for TTR the category $\geq 60\%$ of time will be used as the reference category.

Also, time from AF diagnosis to time of initiation of warfarin treatment will be added as an additional covariate to the Cox's proportional hazards model.

Objective 3: Stratified incidence rates with 95% CIs will be estimated for stroke, systemic thromboembolic events, myocardial infarction, and bleeding events within the strata of other covariates for warfarin patients after stopping warfarin treatment. Warfarin treatment is considered ended if there is more than 2 months gap since last warfarin exposure and INR measurement. Sensitivity analysis with 1 and 3 months gaps will be performed to study the robustness of the definition.

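### Exploratory Objective 2: on the natural reading, the hazard ratio for peri-procedural discontinuation is adjusted for INR, so it is the association INR does not explain rather than the risk the objective asks about

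*Protocol*

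**What the plan says.** Protocol section 2.3 (Objective 2) asks for the risk of stroke, systemic thromboembolic events, myocardial infarction and bleeding "in relation to discontinuation of warfarin treatment due to surgical operations and interventions". It does not ask for risk at a given INR.

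Section 4.1.3 (Objective 2) defines the exposure as a fixed period that "is identified as starting two weeks before and ending two weeks after such procedure". It plans incidence rates inside these periods by the other covariates, and then one comparative analysis: "Also, an indicator variable of the discontinuity period will be added to the Cox's proportional hazards model". No covariate list is given for that model. The planned sensitivity analysis varies the definition of the period, not the model.

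The model referred to has to be found elsewhere. In section 4.1.1, hazard ratios are "estimated separately within the INR levels and TTR categories using the conventional Cox's proportional hazards model adjusting for other covariates". The Cox analyses of Secondary Objective 1 and Exploratory Objective 1 follow the same pattern. Secondary Objective 2 uses closely similar wording for another variable, which "will be added as an additional covariate to the Cox's proportional hazards model".

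Section 4.1 gives two versions of daily INR, the first being "As the previous recorded INR measurement" and the second linear interpolation, with the previous value used when measurements are more than 60 days apart. TTR looks back over 1 to 10 months, or over the last 5 or 10 measurements.

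**The concern.** Section 1.1 itself says that an INR below 2.0 weakens warfarin's protection against stroke. Stopping warfarin for a procedure raises stroke risk by that route, so INR inside the window lies on the path from exposure to event. With daily INR in the model, the indicator compares days inside and outside the window at the same INR level. That leaves whatever INR does not carry, such as the risk of the procedure itself.

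At stake is the objective's only planned comparative estimate. A real excess of stroke that runs through low INR could be shrunk, in the worst case almost to nothing, and read as reassurance about interruption. For bleeding, any reduction due to the lower INR would likewise be removed. The text also leaves open which INR or TTR model hosts the indicator, and the answer depends strongly on that.

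**Working it through.** The protocol states no hazard ratio, power or sample size for this objective, so there is no figure to reproduce. The check asks how far each version of INR or TTR would move the window hazard ratio.

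**Inputs from the protocol.** Window of 14 days either side of the procedure (section 4.1.3); both daily INR versions and the TTR look-backs (section 4.1); 21.7%, 63.6% and 14.7% of INR measurements below, within and above 2.0-3.0 (section 4.2), used for calibration.

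**Inputs assumed.** A hazard ratio *h* of 2, 3 or 5 for INR below 2.0; in the base case, no direct procedure effect, warfarin effect lost from day -4 to day +8, and INR also measured around the procedure. None of these is in the protocol.

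**Step 1, closed form.** Let p1 and p0 be the shares of days with INR below 2.0 inside and outside the window. If hazard depends only on whether INR is below 2.0:

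HR without INR = [1 + p1(h - 1)] / [1 + p0(h - 1)]

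With p1 = 0.70 (assumed), p0 = 0.217 and h = 2, this is 1.70 / 1.217 = 1.40. Conditional on true daily INR it is 1.00, by construction.

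**Step 2, INR as it would be recorded.** Person-day INR histories were simulated for 4,000 patients over 2 years with one procedure each. The window hazard ratio came from Poisson rate regression with constant baseline hazard, which is equivalent to Cox here. TTR was split at 60%.

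| Scenario | No INR/TTR | Interpolated INR | Carried-forward INR | 1-month TTR | 6-month TTR |
|---|---|---|---|---|---|
| h = 2 | 1.29 | 1.02 | 1.17 | 1.23 | 1.29 |
| h = 3 (base) | 1.50 | 1.02 | 1.26 | 1.38 | 1.49 |
| h = 5 | 1.77 | 1.03 | 1.38 | 1.56 | 1.76 |
| h = 3, effect lost day -10 to +14 | 1.95 | 1.18 | 1.52 | 1.77 | 1.94 |
| h = 3, no INR measured in window | 1.49 | 1.53 | 1.49 | 1.50 | 1.49 |
| h = 3, direct procedure effect of 2 | 2.98 | 2.05 | 2.52 | 2.75 | 2.97 |

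**Step 3, consistency of the base row.** INR was below 2.0 on 56.2% of window days and 22.4% of all days. The window is 28/730 = 0.038 of follow-up, so p0 = (0.224 - 0.038 × 0.562) / 0.962 = 0.211. The formula gives (1 + 2 × 0.562) / (1 + 2 × 0.211) = 2.124 / 1.422 = 1.49, against 1.50 simulated.

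**Step 4, share of the association removed in the base row.** On the log scale this is 1 - ln(adjusted HR)/ln(1.50), with ln 1.50 = 0.405:

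- interpolated INR: 1 - 0.020/0.405 = 95%
- carried-forward INR: 1 - 0.231/0.405 = 43%
- 1-month TTR: 1 - 0.322/0.405 = 20%
- 6-month TTR: 1 - 0.399/0.405 = 1%

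**The case against.** The strongest reply is that INR in the host model is inferred. Section 4.1.3 lists no terms, and a covariate list for an exploratory model is ordinary content for the separate analysis plan. The wording also gives some signal the other way: Objective 2 stratifies its rates by the other covariates only, where neighbouring objectives name INR levels and TTR categories. It also lacks the phrase in Secondary Objective 2 that calls the added variable an additional covariate. This stands as a limit on certainty. It does not remove the point, because the sentence adds the indicator to an existing model and the protocol defines no Cox model without INR or TTR.

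The second reply is that near-total attenuation is a special case, and this stands in full. TTR is trailing, carried-forward INR lags the drop, and INR may not be measured in the window at all. An adjusted ratio of exactly 1.00 follows only from assuming that hazard depends on INR alone and that INR is known every day. With a direct procedure effect of 2, the adjusted ratio is 2.05, which nobody would read as no excess risk.

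Third, the rates inside the window are not conditioned on INR. They can be set informally beside the section 4.1.1 rates for the same endpoints. That describes total risk but is not a planned comparison with an interval.

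Finally, dropping INR has its own price. The window is fixed and nothing checks that warfarin was stopped, so the unadjusted ratio mixes interruption with the procedure: 2.98 in the last scenario, against 1.50 for interruption alone.

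**Conclusion.** The point holds in a limited form. On the natural reading, the planned hazard ratio is the association of the discontinuity period with events that INR does not explain, which is a different quantity from the one section 2.3 asks for. Attenuation is near complete with interpolated INR measured around the procedure, partial with carried-forward INR or one-month TTR, negligible with six-month TTR, and absent if INR is not measured in the window. For one assumed association of 1.50, the protocol's own exposure versions give anything from 1.02 to 1.49. These sizes rest on assumed effect sizes, interruption lengths and measurement patterns.

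A reader might infer more: that the model certainly contains concurrent INR or TTR, and that a harmful interruption will therefore return a ratio near 1. The documents support neither. The model's terms are not listed, TTR is not a concurrent measure, and a ratio near 1 needs well-recorded INR and no direct procedure effect.

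Priority is low. The objective is exploratory, and no primary analysis is affected.

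**What to change.** In section 4.1.3, Objective 2, replace the sentence on the indicator with text to this effect:

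> The main result is the hazard ratio for the discontinuity-period indicator from a Cox model with the other covariates at baseline and without concurrent daily INR level or TTR. A model that also contains daily INR level, with the INR version stated, is reported as secondary and labelled as the part of the association not explained by INR. Because the period is fixed around the procedure and interruption is not verified, the main hazard ratio combines interruption with the procedure's own risk.

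Carrying the last INR or TTR before the window into the main model is not advised as a substitute. Most person-time belongs to no window, so that covariate would be undefined there.

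The cost is a short text change and one extra model on data already held. The drawback is the mixing of interruption and procedure risk, which the wording above discloses but does not resolve.
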